#### **Describe other resources available to conduct the research.**

**13.2** *Describe the time and effort that the Principal Investigator and research staff will devote to conducting and completing the research.*

Response: [name] will contribute 1.5 months to the study. [name] will contribute .5 [name] will contribute 1.5 montsh. The study also budgets for a ½ time project manager and also a graduate student line.

*13.3 Describe the availability of medical or psychological resources that subjects might need as a result of anticipated consequences of the human research, if applicable.*

Response: All links to the study survey will include a referral list and contact information for participants to reach someone for additional support in the event that they find the reporting of psychosocial stressors/traumatic events stressful or upsetting. This referral list will explicitly include local and national resources for both trauma and also substance misuse. In addition, as we have done in the previous web-based studies, we have a “**Request for Contact**” button that appears at the end of the web survey. Participants are instructed to click on this button if they are distressed and would like to talk to a member of the project staff. Clicking this will generate an e-mail to our staff, and [name] will contact the participant within two business days. This will give participants who are distressed and/or who have experienced a recent event to discuss both treatment and reporting options with a mental health professional.

*13.4 Describe your process to ensure that all persons assisting with the research are adequately informed about the protocol, the research procedures, and their duties and functions.*

Response: See above and also the Study Timeline. There is time allotted for training of staff in study procedures, including necessary duties and functions.

## **14.0 Other Approvals**

*14.1 Describe any approvals that will be obtained prior to commencing the research (e.g., school, external site, funding agency, laboratory, or biosafety).*

Response:

**N/A:** This study does not require any other approvals.

## **15.0 Provisions to Protect the Privacy Interests of Subjects**

*15.1 Describe how you will protect subjects' privacy interests during the course of this research.*

Response: Participants will be assessed at three points annually, for three weeks each (a total of 9 weekly assessments per year). A more comprehensive baseline assessment will precede the first of the three weekly assessments. In an effort to prevent or minimize discomfort or embarrassment in responding to questions we will reiterate our procedures for protecting participant confidentiality in on-line questionnaires. Participants will be informed that study participation is entirely voluntary, and that they may choose not to participate without any consequence to them. Further, participants also will be informed that they may skip specific items within the online survey if they so choose. Detailed procedures for protecting electronic data are described within the body of this proposal, and include the creation of random ID numbers which are later hooked into a “hash ID”. Thus, at no point are identifying information and participant data linked in cyberspace. We will further safeguard against breaches of confidentiality by coding participant data by ID number rather than by name and by keeping information linking these ID numbers to specific individuals in separate files (i.e., identifying information is stored in a separate electronic file with a separate password, accessible only to project staff). Further, no individuals will be identified by name nor will any identifying information be offered when presenting data in lectures, seminars, professional presentations, or papers. Finally, we will obtain a Certificate of Confidentiality from NIH for this study, as an additional protection of confidentiality of data. Participants will be informed that this is in place. All links to the study survey will include a referral list and contact information for participants to reach someone for additional support in the event that they find the reporting of psychosocial stressors/traumatic events stressful or upsetting.

Finally, participants may be concerned about the confidentiality of their responses. Data show that under-reporting of substance use is reduced when participants believe assurances of confidentiality

and you have cultivated a trusting relationships with them (Harell, 1997; Winters et al., 1991, Wish et al., 1997). Both of these necessary conditions will be in place. First, we will have a Certificate of Confidentiality in place, and will describe this to participants in the consent form. We expect that this will both minimize risk of any breach of confidentiality, and also ease any concerns that participants may have about the security of their data. Second, as we have followed this sample over approximately 10 years, assessing –among other things - illicit behaviors such as substance use and other risk behaviors (e.g., delinquency), we are confident that a strong rapport has been established with these participants.

**15.2 Indicate how the research team is permitted to access any sources of information about the subjects.**

**Response:** Participant information will be stored by participant study ID number, and not by any identifying information. The link between participant data and identifying information will be stored separately, in a “master list” that will be stored on a password-protected computer. The document itself also will have a password. Only project staff will have access to this information.

## **16.0 Data Management and Analysis**

**16.1 Describe the data analysis plan, including any statistical procedures. This section applies to both quantitative and qualitative analysis.**

### **Analytic Plan**

Aim 2: The goal of the Stage 2 open trial is to evaluate the feasibility of the intervention, as well as to generate suggestions for improving and refining it. To this end, the feedback obtained through the Stage 2 open trial and dyad interviews will be analyzed primarily using qualitative data analysis. All qualitative data analysis will be transcript-based, using complete interview transcripts and observer notes as the original data sources. Given that our purpose is to make sense of participants' feedback and suggestions for improving the intervention, content and thematic analysis will be used to analyze transcript data (see Braun & Clarke, 2006; Hsieh & Shannon, 2005). The dyad and not the individual will be the unit of analysis (Krueger & Casey, 2012). We will use Nvivo software (22.nvivo.com) for data analysis. At least two coders will read through the transcripts and develop and refine a series of codes through an iterative process. Disagreements will be resolved through team discussion and final codes to be entered into Nvivo as “nodes”. Node development will reflect the targeted areas of feedback and will be organized around improving relevance and feasibility of the intervention (e.g., barriers, effects of alcohol, ease of implementation). Once entered, the Nvivo program will be used to sort and organize information chunks into thematic categories. Themes will be reviewed and discussed by the investigators and final kappa agreement will be computed. Using Nvivo, a series of headings will be generated, each corresponding to themes identified in the focus groups. We also will use Nvivo's “query” function to search interview data to examine respondents' reactions to content and feasibility domains of the FMI. In Stage 2, we also will review quantitative summary data from self-report assessments (ratings of feasibility, acceptability) for consideration of continued modification.

### **Aim 3:**

*Data preparation.* We will examine patterns of missing data, research dropout rates, therapist adherence and competence, distributional properties of our measures, and correlations among outcome measures. Though we expect some missing data due to attrition, this will be minimal as we will be using rigorous participant retention procedures that have proven effective in our prior work. Importantly, our analytic approach (below) will allow us to include cases with missing data. Given the short follow-up and the fact that we are focusing on close friend dyads, we expect minimal missing data. However, we will attempt to follow up with everyone, and in the case of one friend dropping out we will attempt to determine whether the intervention played any role in study attrition. We will

examine for FMI and control group differences on baseline measures and demographics, and if differences emerge, we will include the relevant variables as covariates in analysis.

*Treatment Feasibility and Fidelity.* Descriptive analyses of adherence data, refusal rates, follow-up rates, and participant evaluations will be used to guide possible changes in the intervention and to provide information on feasibility and acceptability. Decisions about possible intervention changes will be made with consideration of qualitative data (analysis described above) and investigator input. As noted, we will collect data on fidelity to ensure that the FMI was administered according to protocol and consistent with MI spirit.

*Outcome analyses.* The primary goals of Aim 3 are to evaluate whether (1) FMI increases readiness, reduces perceived barriers, and increases alcohol knowledge and strategies post-intervention and over the follow-up (2) FMI increases the implementation of friend-based assault-protective behaviors (FAPB) in our 3-month follow-up, and (3) changes in readiness, perceived barriers, alcohol knowledge and strategies are associated with implementation of FAPDs at 3-month follow-up (potential mechanisms). We will also examine if quality of the dyad relationship changes as a function of the intervention. Increases would suggest strengthening of the relationship as a function of the intervention, and declines would indicate iatrogenic effects. Whether increases in implementation of behavioral strategies are associated with reduced rates of sexual victimization will also be examined. Examination of sexual victimization is exploratory, as victimization rates are expected to be relatively low over the short follow-up period (i.e., approx. 30% across 3 months; Parks et al., 2008). In secondary analyses, parallel analyses will also be done with alcohol use as an outcome variable. Given the pilot nature of the R34 mechanism and the smaller sample size, we will focus analysis on effect sizes and whether effects are in the proposed direction. Effect size estimates can be unreliable in small pilot studies (Kraemer et al., 2006); thus, we will report effect sizes ranges (95% confidence bands).

A prominent feature of our design is that individuals are nested within dyads, and this necessitates a data analytic approach that can accommodate nested data structures. Hence, our Aim 3 analyses are built around hierarchical linear models (HLMs). First, we will evaluate group differences on variables from our first post-intervention assessment (i.e. perceived barriers, readiness, alcohol knowledge and strategies, and implementation of FAPBs) using a two level model (individuals nested within dyads). Treatment will be dummy coded (FMI vs. waitlist control group) and included as a level two covariate. Second, we will utilize all data from our three month follow-ups and repeat these analyses using a three-level model (6 repeated measures nested within individuals, and individuals nested within dyads). In these models treatment will be included as a level three covariate. We will use  $\beta$  to describe effect sizes (Cohen, 1988; Selya et al., 2012).

Our burst design provides a rich opportunity to examine whether changes in target constructs of interest (e.g., barriers, skills, alcohol knowledge and strategies) are associated with implementation of FAPBs. For these analyses we will combine the post-intervention data from our FMI and WLC groups after the latter has completed the intervention and follow-up assessments. Combining groups will increase our sample size and provide more stable estimates of effect sizes. For these analyses we will include reports of past week protective behavioral strategies just prior to the intervention and weekly aggregates of protective behavioral strategies from our three-month follow-up yielding 7 repeated measures nested within individuals and individuals nested within dyads. Using growth models, we will model change in readiness, perceived barriers, alcohol knowledge and strategies, and implementation of FAPBs. Effect sizes characterizing change will be computed in two ways: 1). Computing a difference score using baseline and the first follow-up divided by the standard deviation of the difference score, and 2). A difference score using baseline and the last assessment of the follow-up divided by the standard deviation of the difference score (Gibbons et al., 1993; Morris & DeShon, 2002). Individual level intercepts and slopes will be output from these growth models and this will allow us to examine correlations between slopes and intercepts. We expect that reductions in perceived barriers (better self-efficacy, fewer interpersonal concerns), and increases in readiness will be positively related to implementation of FAPBs. Our growth models will

also allow us to include individual characteristics (e.g. assault history, drinking history, relationship, responsibility) to examine their association with change in perceived barriers, skill implementation, etc. (e.g., prior history of sexual assault is related to more or less change in variables our intervention is expected to impact).

In exploratory analyses, we will examine whether increases in implementation of FAPB from baseline to follow-up are associated with rates of sexual victimization. For these analyses we collapse our follow-up data into dichotomous variable indicating whether sexual victimization occurred. Using a two-level HLM (individuals nested within dyads), this dichotomous outcome will be regressed on the intercepts and slopes from our growth models of FAPBs (described above). Steeper increases in FAPBs are expected to be associated with lower likelihood of sexual victimization at follow-up controlling for baseline levels of sexual victimization. Odds ratio will be used to describe the effect size. Data from stakeholder and exit interviews will be analyzed using qualitative data analytic techniques.

#### *16.2 If applicable, provide a power analysis.*

**Power Estimates and Sample Size.** This is an intervention development project. As such, the focus is on feasibility rather than on statistical significance. For this reason, as described above, our analyses will focus largely on the derivation of effect sizes to inform parameter estimates for future studies, and to gauge clinical significance of the intervention. Still, we will conduct inferential tests. For these, with a sample of 88 in Study 3, we will be powered to detect “moderate” to “large” intervention effects.

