## **Stage 2: Preliminary Implementation and Further Refinement**

**Aim 2.** Conduct an initial open trial of this intervention with short-term (4-week) follow-up, and then modify based on feedback and outcomes.

1. We will conduct an open trial of our FMI intervention (friend dyads n=10, 20 women) and comprehensively evaluate the intervention via multiple methods (investigator observations, open-trial sessions, feedback interviews) during and post-intervention.
2. We will use feedback from the open trial to further refine the FMI intervention.

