**Stage 3: Intervention Testing**

**Aim 3.** Conduct a mini-trial with 3-month follow-up via weekly assessments to examine changes in target attitudes (readiness, barriers) and behaviors (friend-based assault prevention behavior skills). We also will examine knowledge and strategies pertaining to the role of alcohol in helping behavior, and will test whether drinking influences the implementation and efficacy of this intervention.

Twenty-four friend dyads will participate in the FMI along with 24 wait-list control dyads (total of 48 dyads). We will compare groups on outcomes at post-intervention and at bi-weekly 3 month follow-ups, and also examine within subjects change. Given the pilot nature of the R34 mechanism and the smaller sample size, we will focus on whether effects are in the expected direction and whether the strength of effect sizes are of practical magnitude. We expect participants receiving the FMI to demonstrate significant increases in readiness, and engagement in FAPBs and alcohol strategies, and decreases in perceived barriers (improved self-efficacy, relationship concerns), at post-intervention and over the 3-month follow-up. We will also use our follow-up data to provide a rich description of the role of alcohol in implementing FAPBs, and whether the FMI reduces the impact of alcohol use. In exploratory analyses, we will examine whether the intervention may be associated with decreased assault risk, as well as decreased drinking (see **Data Analysis Plan**).

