**Stage 3 Procedures:**

*Intervention: FMI Mini-Controlled Trial with Intensive Follow-Up*

In this stage, we will test the finalized FMI (see **Screening, Eligibility, and Recruitment** above). To do this, we will contrast outcomes among those in this trial (N=24 dyads) with 24 pairs of friend dyads (total dyad N=48) who are randomly assigned to a wait list control condition.

The FMI will consist of a single session. Sessions will be offered on many days and times across the week to accommodate variability in student schedules. Each session will begin with a baseline assessment. In this session, women will be provided with the refined intervention protocol and will have the opportunity to role play and practice implementing the skills and strategies. Following the intervention, participants will be encouraged to utilize the skills and strategies presented in the intervention over the next 12 weeks, whenever they are out with their friend in a social context.

Dyad pairs assigned randomly (stratified on drinking levels, sexual assault history, and age) to the wait list control condition will be assessed once at baseline and again 12 weeks post-baseline. Assessment measures (baseline, 12 weeks) will mirror those administered to women in the FMI condition. At the completion of the 12 week “wait list,” participants will be administered the FMI and followed for 12 weeks. Comparison of outcomes across conditions will allow for stronger inferences about the efficacy of the intervention, will allow for examination of measurement reactivity, and will increase our sample size to examine within person change.

*Follow-up Assessments.* We will conduct bi-weekly online post-intervention assessments (with the first assessment to occur within 2 weeks of FMI completion) for 12 weeks. The bi-

weekly structure will optimally capture women's experiences applying strategies from the intervention. Participants will be reminded of follow-up assessments by phone, text, and email prompt. Individual members of the dyad will be interviewed in the unlikely event that the other member is lost to follow up over the brief follow-up period. At the end of the 12 weeks, participants will be contacted for an exit interview.

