## **5.0 Local Number of Subjects**

5.1 *Indicate the total number of subjects that will be enrolled or records that will be reviewed locally.*

Response: The total number of participants across the three studies will be 128.

5.2 *If applicable, indicate how many subjects you expect to screen to reach your target sample.*

Response: 175

5.3 *Justify the feasibility of recruiting the proposed number of eligible subjects within the anticipated recruitment period. For example, how many potential subjects do you have access to? What percentage of those potential subjects do you need to recruit?*

Response: Participants will be recruited from the nearly a dozen colleges in the greater Buffalo area. The University at Buffalo alone has over 30,000 students, approximately ½ of whom are women. Given the large student population from which we will draw from, and the fair financial remuneration that participants will receive for participation, achieving our target N within the proposed timeframe is highly feasible.

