## 11.0 Study Timelines

11.1 *Describe the anticipated duration needed to enroll all study subjects.*

Response: We expect that all study subjects will be enrolled within the first 2.5 years of the project, so by January of 2020.

11.2 *Describe the duration of an individual subject's participation in the study. Include length of study visits, and overall study follow-up time.*

Response: Once enrolled, participants will be followed over a period of 3 months.

11.3 *Describe the estimated duration for the investigators to complete this study.*

Response: See timeline, below.

Funding Period	Staffing & Training	Stage I FMI Development	Screening and Recruitment	Stage I: Focus Groups (N= 6-8 per group)	Stage 1 Review and Modification	Stage 2: Open Trial (N= 16)	Short-term Follow -Up	Stage 2 Review and Modification	Stage 3 Intervention mini-RCT (N=92) Intervention WLC conditions	3 MO FU (weekly online assmts)	Data Analysis and Report Writing
Sept '18-Dec '18	X	X									
Jan 19-Mar '19		X	X	X							
April '19-June '19			X	X	X						X
July '19-Aug '19					X						X
Sept '19-Dec '19	X		X			X	X				X
Jan '20-March '20			X			X	X	X			X
April '20-June '20							X	X			X
July '20-Sept '20	X		X						X		X
Oct 20-Dec '20	X		X						X	X	X

Jan '21- Mar '21			X						X	X	X
April '21- June '21			X						X	X	X
July '21- Aug '21										X	X

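### Stage 3 is 96 women in the design, 92 in the timeline and 88 in the power statement, and the stated enrolment of 128 fits the 88 rather than the design, which totals 136

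*Combined protocol and SAP*

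**What the plan says.** The size of Stage 3 appears in four places in the protocol.

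- Section 4, Stage 3: Intervention Testing: "Twenty-four friend dyads will participate in the FMI along with 24 wait-list control dyads (total of 48 dyads".
- Section 4, Stage 3 Procedures, on the control arm: "24 pairs of friend dyads (total dyad N=48". The words before the bracket are loose, but the bracketed total confirms 48 dyads overall.
- Section 11.3, timeline table: "Stage 3 Intervention mini-RCT (N=92".
- Section 16.2, power statement: "with a sample of 88 in Study 3, we will be powered to detect".

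The other stages are sized as follows. Section 4 describes about four focus groups of five women for Stage 1, giving n=20, and for Stage 2 an open trial with "friend dyads n=10, 20 women". The timeline table differs on both: "Stage I: Focus Groups (N= 6-8 per group" and "Stage 2: Open Trial (N= 16".

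Section 5.1, which asks for the number of subjects to be enrolled, answers: "The total number of participants across the three studies will be 128".

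On attrition, section 16.1 (Aim 3, data preparation) expects some missing data from dropout, calls it minimal, plans for the case where one friend leaves, and says the models can use incomplete cases. It gives no rate. The Statistical Analysis Plan repeats this and gives no sample size.

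**The concern.** The same trial is given three sizes, and the enrolment total is not the sum of the stage sizes in the design section. Two things are at stake. First, 128 is the enrolment figure in the application to the ethics board, and carrying out the design would exceed it. Second, the power sentence refers to a number that the design does not randomise, and nothing says whether 88 is an enrolled or an analysed number. Study staff have no single target at which to stop assigning dyads (44, 46 or 48), and a later report could not show from these documents whether the planned size was reached.

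**Working it through.** **Inputs.** Stage 3: 48 dyads (section 4), 92 (section 11.3), 88 (section 16.2). Stage 1: about 20 women (section 4). Stage 2: 20 women (section 4), 16 (section 11.3). Total: 128 (section 5.1). A dyad is two women.

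**1. Unit of 92 and 88.** Read as dyads, they would be 184 and 176 women, each more than the 128 stated for all three stages. They must count women.

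| Source | Women | Dyads | Dyads per arm |
|---|---|---|---|
| Section 4 | 48 × 2 = 96 | 48 | 24 |
| Section 11.3 | 92 | 92 / 2 = 46 | 23 |
| Section 16.2 | 88 | 88 / 2 = 44 | 22 |

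**2. Reproducing the 128.** With the text sizes for Stages 1 and 2, 20 + 20 + 88 = 128. The figure in section 5.1 is reproduced exactly by the Stage 3 number in section 16.2.

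**3. Total under the design.** 20 + 20 + 96 = 136. The excess over section 5.1 is 136 − 128 = 8 women, and 8 / 128 = 6.3%.

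**4. Could Stage 1 absorb the difference?** To reach 128 with 96 in Stage 3 and 20 in Stage 2, Stage 1 would have to be 128 − 96 − 20 = 12 women, against a stated n of 20.

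**5. Could dropout explain it?** Going from 96 to 88 implies a loss of 8 / 96 = 8.3%; from 96 to 92, 4 / 96 = 4.2%. Neither rate is stated.

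**6. The timeline on its own terms.** It gives no number of focus groups. With the text's four groups, 6 to 8 per group is 24 to 32 women, so the timeline basis totals 24 + 16 + 92 = 132 to 32 + 16 + 92 = 140. That is not 128 either.

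**7. Consequence for power.** Section 16.2 gives no significance level, power level or within-dyad correlation (ICC), so these are assumed: two-sided 5%, 80% power, ICC 0 to 0.6. With N women in total, in dyads of two, the detectable standardised difference is (1.960 + 0.842) × √(2 × (1 + ICC) / (N / 2)).

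| ICC | N = 88 | N = 96 | Difference |
|---|---|---|---|
| 0 | 2.802 × √(2 / 44) = 0.597 | 2.802 × √(2 / 48) = 0.572 | about 0.03 |
| 0.6 | 2.802 × √(3.2 / 44) = 0.756 | 2.802 × √(3.2 / 48) = 0.723 | about 0.03 |

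This is a sensitivity check only. None of these values is offered as text for the plan.

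**The case against.** The strongest reply is that 88 is the number expected to be analysed. Section 16.1 does expect some attrition, and a loss of 8.3% could be called minimal. That cannot be ruled out for section 16.2 taken alone, but no section says it. It also does not rescue section 5.1, which counts enrolled subjects and yet matches 88.

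A second reply is that the size hardly matters in a development project. Section 16.2 puts feasibility ahead of significance, and section 16.1 concentrates on effect sizes with confidence bands. This stands as far as power is concerned, and it limits the severity.

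A reader might also infer more than the documents support:

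- *That 128 is an addition error.* It is not. Sections 5.1 and 16.2 agree with each other on the text's Stage 1 and Stage 2 sizes. There is one Stage 3 discrepancy carried into the total, and separately a timeline table that differs.
- *That the true total might be 132 (20 + 16 + 96), or that 128 comes from 20 + 16 + 92.* Both sums mix the text's Stage 1 with the timeline's Stage 2, and no section states either combination. With Stage 1 only approximate, a gap of 4 women is also less than one focus group of five.
- *That the trial is underpowered, or the power claim false.* The assumed range of 0.57 to 0.76 SD is compatible with the loose wording of section 16.2 at either size.
- *That 128 is a ceiling whose breach has a regulatory consequence.* The documents state the number but do not call it a cap.

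**Conclusion.** Wrong as written; it should be fixed. The design fixes Stage 3 at 96 women, while the timeline says 92 and the power statement 88, with nothing to reconcile them. On the text sizes the design totals 136 women against the 128 stated, about 8 women or 6.3% more. The word about is needed because Stage 1 is given only approximately. That the 88 was carried into section 5.1 is an inference from the exact match, not something the documents say. The timeline conflicts with the text on Stage 2 as well (16 against 20 women) and on focus-group size (6 to 8 against 5). The point concerns consistency and the enrolment total. No analysis model or conclusion changes, and the choice between 88 and 96 moves the detectable difference by only about 0.03 SD under the assumptions above.

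**What to change.** State one size per stage, in dyads and in women, and use it in sections 4, 5.1, 11.3 and 16.2, with a total that adds up. There are two consistent ways to do so with the text sizes for Stages 1 and 2.

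- *Keep the 48 dyads.* Stage 1, about 20 women; Stage 2, 10 dyads (20 women); Stage 3, 48 dyads, 24 per arm (96 women); total 136. Section 5.1 becomes 136. Section 16.2 uses 96, or says that 88 is the expected analysed number and gives the dropout allowance behind it.
- *Keep the total of 128.* Change both Stage 3 statements in section 4 to 44 dyads, 22 per arm (88 women).

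In either case, bring the Stage 1, 2 and 3 entries of the timeline table into line. The cost is wording in four sections, plus a corrected enrolment total in the application if 48 dyads are kept. That option adds no participants beyond those the design already describes. The other gives up four dyads and about 0.03 SD in the detectable difference.

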A prominent feature of our design is that individuals are nested within dyads, and this necessitates a data analytic approach that can accommodate nested data structures. Hence, our Aim 3 analyses are built around hierarchical linear models (HLMs). First, we will evaluate group differences on variables from our first post-intervention assessment (i.e. perceived barriers, readiness, alcohol knowledge and strategies, and implementation of FAPBs) using a two level model (individuals nested within dyads). Treatment will be dummy coded (FMI vs. waitlist control group) and included as a level two covariate. Second, we will utilize all data from our three month follow-ups and repeat these analyses using a three-level model (6 repeated measures nested within individuals, and individuals nested within dyads). In these models treatment will be included as a level three covariate. We will use  $\beta$  to describe effect sizes (Cohen, 1988; Selya et al., 2012).

Our burst design provides a rich opportunity to examine whether changes in target constructs of interest (e.g., barriers, skills, alcohol knowledge and strategies) are associated with implementation of FAPBs. For these analyses we will combine the post-intervention data from our FMI and WLC groups after the latter has completed the intervention and follow-up assessments. Combining groups will increase our sample size and provide more stable estimates of effect sizes. For these analyses we will include reports of past week protective behavioral strategies just prior to the intervention and weekly aggregates of variables of interest from our three-month follow-up yielding 7 repeated measures nested within individuals and individuals nested within dyads. Time will be included as a level-1 covariate, and we will

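### Section 16.2 claims power for 'moderate' effects without defining them or allowing for dyads; if moderate means d = 0.5, between-arm power is about 47–55% with 44 dyads

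*Combined protocol and SAP*

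**What the plan says.** Section 16.2 first says that the project is about feasibility and about effect sizes for later studies. It then says that inferential tests will be run, and that for these "with a sample of 88 in Study 3, we will be powered to detect" what it calls "moderate” to “large” intervention effects". That is the whole power statement. It contains no calculation.

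Other parts of the documents bear on it:

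- **Unit of randomisation.** Stage 3 Procedures assign dyads, not women, to the waitlist.
- **Model.** The SAP states: "A prominent feature of our design is that individuals are nested within dyads, and this necessitates a data analytic approach". Treatment enters the first model as a level-two (dyad) covariate.
- **Sample size.** The Stage 3 aim reads: "Twenty-four friend dyads will participate in the FMI along with 24 wait-list control dyads (total of 48 dyads", which is 96 women. The timeline in section 11.0 has "Stage 3 Intervention mini-RCT (N=92". Section 5.1 says "The total number of participants across the three studies will be 128".
- **Reporting.** Because effect sizes from small pilots are unreliable, "we will report effect sizes ranges (95% confidence bands".

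**The concern.** The power statement counts women, but the information on the treatment effect comes from dyads. Two close friends who drink together and receive the intervention together are likely to give correlated answers, so 88 women carry less information than 88 independent people. The rest of the plan recognises this and section 16.2 does not. Even before clustering, 44 women per arm is a small number for a conventional moderate effect.

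The stake is how a null result is read. The Stage 3 aim expects significant changes, and section 16.2 says the effect sizes will inform later studies. A reader who has been told that the trial can detect moderate effects may take a non-significant result as evidence against one.

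**Working it through.** **Inputs from the documents**

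- 88 women, so 44 dyads, taken as 22 per arm (section 16.2). The alternative is 48 dyads, 24 per arm (Stage 3 aim).
- The section 5.1 total does not settle which is right: 20 + 20 + 88 = 128, but 20 + 16 + 92, using the timeline's Stage 2 and Stage 3 figures, is also 128.
- Randomisation is by dyad, with treatment at dyad level. Degrees of freedom are therefore dyads − 2: 42 or 46.

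**Inputs the documents do not give (assumptions)**

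- Moderate is d = 0.5 and large is d = 0.8.
- The test is two-sided at 5%, and being powered means 80%.
- ICC is 0.2–0.5, with 0 shown as the most favourable case among non-negative values.
- There is no baseline adjustment, and outcomes are compared at a single time point.

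**The plan's own figure.** There is no power percentage to reproduce.

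**Step 1: ignore clustering.** An ordinary t-test on 44 independent women per arm (86 df) has 64% power at d = 0.5. Reaching 80% would need 2 × (1.960 + 0.842)² / 0.5² = 62.8, so 63 women per arm (126 in all), before any clustering.

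**Step 2: allow for dyads.** In SD units, the mean of two women has variance (1 + ICC)/2. With k dyads per arm, the standard error of the difference is √[2 × (1 + ICC)/2 ÷ k] = √[(1 + ICC)/k]. Example with k = 22 and ICC = 0.5: √(1.5/22) = 0.261, so the noncentrality at d = 0.5 is 0.5/0.261 = 1.91, against a critical t of 2.018. Power is 46.5%.

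| ICC | 44 dyads: power, d = 0.5 | 80%-power d | Power, d = 0.8 | 48 dyads: power, d = 0.5 | 80%-power d |
|---|---|---|---|---|---|
| 0 | 63.0% | 0.61 | 95.6% | 66.9% | 0.58 |
| 0.2 | 55.2% | 0.67 | 91.7% | 59.1% | 0.64 |
| 0.3 | 52.0% | 0.70 | 89.5% | 55.7% | 0.67 |
| 0.5 | 46.5% | 0.75 | 84.9% | 49.9% | 0.72 |

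The timeline's 92 women give 65.0% at ICC 0 and 57.2% to 48.2% at ICC 0.2 to 0.5.

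**Step 3: interval width.** The 95% half-width is t × SE. With 44 dyads it is 2.018 × 0.2335 = 0.47 SD at ICC 0.2 and 2.018 × 0.2611 = 0.53 SD at ICC 0.5. With 48 dyads it is 2.013 × 0.2236 = 0.45 SD and 2.013 × 0.2500 = 0.50 SD.

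**Step 4: vary the assumptions at d = 0.5.**

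- A one-sided 5% test at ICC 0 gives 74.6% (44 dyads) or 77.9% (48).
- A baseline covariate with r = 0.5 gives 58–68% with 44 dyads at ICC 0.5–0.2. With r = 0.7 it gives about 75–83%.

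**Step 5: vary the meaning of moderate, 44 dyads.**

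- If moderate means a correlation of 0.3, then d = 2 × 0.3/√(1 − 0.09) = 0.63. Power is 82% at ICC 0, 72% at 0.3 and 65% at 0.5.
- If it means f² = 0.15, then for two equal arms d = 2√0.15 = 0.77. Power is 94% at ICC 0, 88% at 0.3 and 83% at 0.5.

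**The case against.** The strongest reply is that the plan never says what moderate means. The effect-size guide cited under Outcome analyses is, by its title in the reference list, a guide to Cohen's f². On the f² = 0.15 reading the claim is met at every ICC tried in Step 5. This stands. A reader might infer that the claim is simply false, or that an arithmetic error has been found. The documents support neither, because they define no metric and show no calculation to check.

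Other replies stand only in part:

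- **Baseline adjustment.** A strong covariate would bring power to about 80%. But the SAP's Data preparation paragraph adjusts only where the arms turn out to differ at baseline, so no gain in precision is planned.
- **Six follow-ups.** Under Stage 3 Procedures the waitlist is assessed only at baseline and 12 weeks before it receives the intervention, so six control waves are not available for the randomised contrast. Even if they were, averaging six waves with between-wave correlation 0.5–0.7 (an assumption) would give about 58–78% at ICC 0.5–0.2 with 44 dyads.
- **Pooled pre–post analysis.** Combining both arms after crossover gives 96% power or more for a standardised change of 0.5, and section 16.2 does not name the between-arm contrast. But the pooled analysis is not the randomised comparison, and the plan presents it as a study of change and its correlates.
- **Pilot status.** The plan puts effect sizes, direction and intervals ahead of significance. This stands, and it limits the harm: a reader shown an interval of about ± 0.5 SD is less likely to over-read a null result.

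**Conclusion.** The power statement is unsupported as written. For the between-arm comparison it does not hold at the moderate end if moderate means d = 0.5. Under a two-sided 5% test, an 80% target and no baseline adjustment, power is 63% with no clustering and about 47–55% at ICC 0.2–0.5 with 44 dyads, or 67% and 50–59% with 48. The shortfall therefore does not depend on the assumed ICC, or on which of the three Stage 3 sample sizes is right. It does depend on reading moderate as d = 0.5 and on the absence of a strong pre-specified covariate.

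The large end is not in dispute: d = 0.8 is covered at 85–92% with 44 dyads at the same ICC range. Nor should the result be read as showing that the trial is too small for its purpose, since feasibility and estimation are the declared aims. The consequence is modest and concerns how a non-significant result would be interpreted.

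**What to change.** Replace the last sentence of section 16.2 with one that defines the metric and gives the detectable effect for the between-arm contrast at a single named time point:

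> Two-sided 5%, dyads as the randomised unit, assumed within-dyad ICC 0.2–0.5, no baseline adjustment: with 44 dyads, 80% power for d of about 0.67–0.75, 47–55% power for d = 0.5, and a 95% CI half-width of about 0.47–0.53 SD. [With 48 dyads: d of about 0.64–0.72, 50–59% and 0.45–0.50 SD.] A non-significant result does not rule out d = 0.5.

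Keep only the line that matches the Stage 3 sample size once 88, 92 and 96 have been reconciled. Name the time point so that it agrees with both Stage 3 Procedures and Outcome analyses. At present the first assesses waitlist dyads only at baseline and 12 weeks, while the second analyses the first post-intervention assessment and then six waves. If the investigators intend another metric, such as f², or a pre-specified baseline covariate, they should say so and recompute.

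The cost is one sentence and a less favourable stated figure. No extra participants or assessments are needed.
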